2.1 Primary objective

To evaluate the safety of everolimus compared with placebo in patients with PTEN mutations focusing on NCI CTCAE Grade 3 and 4 adverse events, serious adverse events, and Grade 3 and 4 laboratory toxicities. The primary endpoint will be study drop-out rate due to side effects, comparing everolimus vs. placebo. Based on the published literature and our experience in prior TSC trials we hypothesize that the drop-out rate due to side effects in those receiving everolimus will be similar to those in the placebo group with minimal effect size (< 10% difference). We will also determine the frequency of adverse events by type and severity. We predict that the rate of adverse events will be no more than 10% higher in the everolimus group compared to placebo, but overall severity will be minimal.

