Tests that will be conducted during the blinded treatment phase include laboratory tests for safety, physical exams (including a neurological assessment), vital signs, and neuropsychological assessments. If unforeseen circumstances (i.e., unexpected personal reasons) prevent the patient from complying with the established visit schedule, the site can re-schedule the visit (within \pm 14 days of the expected visit date). The reason(s) for any visit or treatment delays will be documented in the CRF for the appropriate visit. All on-site visits (screening,

baseline, month 1, month 3, and month 6) must be completed by the participant, and any missed visits would warrant termination from the study. A summary of the neuropsychological results may be made available at study completion.

At the end of the double-blind phase (or early termination), the treatment code will be broken and the participant will be informed of their assigned treatment arm, using the process outlined in the 7904 Manual of Procedures. Participants who received the active compound will enter the follow-up phase of the study (section 4.5) and will be referred back to their treating physicians. Individuals who were in the placebo group will be invited to enter Phase B, a 6-month open-label extension trial (section 4.4). The inclusion of the open-label phase may increase the acceptability of the project by families and increase their participation in the primary, controlled trial. All participants that received everolimus during the blinded treatment phase will enter the follow-up phase of the trial and will be referred back to their treating physicians. A summary of patient's participation in the study will be provided, if needed.

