4.6.3 Open-Label Phase Inclusion Criteria

- 1. Patients who completed Double-Blind phase of the study and were assigned to the placebo treatment arm;
- 2. Verbal consent (and assent, as appropriate) obtained prior to any open-label phase study procedures.

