4.7 Early Termination

If the participant, legal guardian, or the study physician make the decision to have the participant exit the study early, a follow-up visit must be scheduled 28 days (+/- 14 days) after termination. At this visit, the study physician should review the patient's medical history, concomitant medications, and the DOTES. If the patient exited the trial due to an adverse event, this event should be reviewed and if it is still present the study team must follow-up with the patient/legal guardian for 56 days or until the event has subsided. At the completion of this follow-up visit, the participant may be unblinded and the results may be disclosed to the participant.

5. Recruitment Methods

Recruitment will leverage the observational study, The Natural History of Individuals with Autism and Germline Heterozygous PTEN mutations, and will occur at 3 sites: Cleveland Clinic, Stanford University, and Boston Children's Hospital, with Cleveland Clinic expected to recruit at least 50% of the sample based on extensive experience with PTEN patients at this site. Over the last 5 years, we have recruited and comprehensively evaluated 35+ patients with PTEN ASD only from referrals to Cleveland Clinic and word of mouth. We anticipate that the majority of these individuals would participate in the proposed study.

We will supplement our current recruitment efforts with several complementary strategies. First, [name] (Cleveland Clinic) has developed a registry of > 400 individuals with PTEN mutations that includes > 50 PTEN cases with ASD or evidence of developmental delay. To date, this registry has not been tapped, but it will be used to recruit individuals for the proposed study. [name] lab also regularly screens individuals at risk of PTEN mutations using an online risk calculator and extensive referral network – growing her registry. Second, the two additional sites, Stanford University and Boston Children's Hospital, also have experience with PTEN ASD patients and have an identified population that is interested in participating in this trial. Both of these sites will also leverage their relevant clinics to advertise and recruit for this study. Third, we have obtained support

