5.1 Retention Strategies

To retain participants throughout the 6-month trial, sites will use procedures that have proven successful in previous studies, such as phone calls to debrief after the most recent visit and phone calls or emails to prepare for the upcoming visit. Individual sites will seek IRB approval for each of the methods that they use prior to distribution. Whenever possible, study staff at each site should also try to schedule study visits on a day that is convenient for the family. Additionally, caregivers, or adult participants, will receive feedback on their child's, or their, neurocognitive profile and changes over time at the end of the trial. Since there is a 50/50 chance of participants receiving everolimus or placebo, it is important for study staff to make sure the family is aware of the open-label phase of the study. Families should also be reminded that all travel expenses, throughout the entirety of the trial, will be covered. Finally, study staff should always express gratitude and thanks to both the patient and his/her family for participation in the study.

6. Description of Study Treatments or Exposures/Predictors

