7.6 Double-Blind Treatment Assignment Unblinding

Prior to the Month 6 visit or early termination, the site will obtain the unblinded treatment assignment via the procedures described in the 7904 Manual of Procedures. At the conclusion of the double-blind phase or early termination, the blind will be broken immediately. Individuals on the active drug will exit the study, and those who were on placebo will be invited to join the open label phase (section 4.4).

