In objective 1, we will examine the safety and tolerability of everolimus by comparing the 1) dropout rates due to side effects, 2) dropout rates for any reason, and the 3) frequency of specific side effects in those receiving everolimus versus placebo. Based on the published literature and our experience in the tuberous sclerosis trial. we predict that the dropout rates due to side effects will be very similar across everolimus and placebo groups (<10% difference). However, we predict that everolimus will cause higher rates of medication-related side effects (≥10% difference) when compared to placebo. We will use chi-square statistics (or Fisher's exact test depending on cell counts) to compare dropout and rates of specific side effects. Statistical significance will be determined using a one-tailed test Type 1 error rate of α=.05, as only increases with everolimus treatment are expected. No false discovery rate correction will be applied because the concern is maximizing sensitivity to any increase in side effect prevalence with everolimus treatment. For dropout rates, we will also compute Kaplan-Meier survival analyses with discontinuation due to side effects or any reason as separate status endpoints. Number of days from baseline to medication discontinuation will be the time variable. Survival analyses are expected to be under-powered due to the generally low dropout rates expected, but these analyses can be useful for describing temporal trends. To ensure any observed group differences are not influenced by other variables or randomization imbalance, cox and logistic regression analysis will also be conducted with and without conditioning on relevant baseline covariates (e.g., demographics, language and cognitive ability, symptom severity).

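### Sections 4.3 and 7.6, as worded, unblind placebo patients who stop early and invite them to open-label everolimus; 4.6.3 and 4.7 do not, and a site following the former could distort the drop-out comparisons.

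*Combined protocol and SAP*

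**What the plan says.** **Invitation and unblinding.** Section 4.3 treats the end of the blinded phase and early termination together: the code is broken, the participant is told the arm, everolimus patients go to follow-up, and "Individuals who were in the placebo group will be invited to enter Phase B, a 6-month open-label extension trial". Section 7.6 also covers both events, has the blind broken at once, and continues: "Individuals on the active drug will exit the study, and those who were on placebo will be invited to join the open label phase". It has the site obtain the assignment before the Month 6 visit or early termination.

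**Eligibility and disclosure.** The first open-label criterion in 4.6.3, repeated in the synopsis, is: "Patients who completed Double-Blind phase of the study and were assigned to the placebo treatment arm". Section 4.7 schedules a visit 28 days (± 14) after early termination and then says: "At the completion of this follow-up visit, the participant may be unblinded and the results may be disclosed to the participant".

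**Family awareness.** Section 5.1, on retention, notes the even chance of placebo and says "it is important for study staff to make sure the family is aware of the open-label phase of the study".

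**Endpoints.** Section 2.1: "The primary endpoint will be study drop-out rate due to side effects, comparing everolimus vs. placebo". Section 17 lists as a further comparison "2) dropout rates for any reason", and adds: "Statistical significance will be determined using a one-tailed test Type 1 error rate of α=.05". Section 17.1 treats any difference of 10% or more as meaningful and reportable.

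**The concern.** Two sites could each point to protocol text and act differently. One following 4.3 or 7.6 would unblind a family that stops at Month 2 and, if the child was on placebo, offer open-label everolimus. One following 4.6.3 and 4.7 would not make the offer and would hold disclosure until the follow-up visit.

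At the first kind of site, a family that believes the child is on placebo has a reason to stop. Such beliefs are plausible: Section 6.3.1 lists stomatitis and acne as very common on everolimus, so their absence is a cue. If these guesses are right more often than chance, the extra exits fall mainly on placebo. That narrows any excess of drop-out on everolimus and moves the result towards the similarity that Section 2.1 predicts.

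The recorded reason for leaving is also exposed. Under 7.6 the site can know the arm before the reason is written down, and that reason decides whether an exit enters the primary endpoint.

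**Working it through.** **1. The passages side by side**

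| Section | Who may enter the open-label phase | When an early terminator is unblinded |
|---|---|---|
| 4.3 | Placebo patients; completion not required | At early termination |
| 7.6 | Placebo patients; completion not required | Immediately |
| 4.6.3 and synopsis | Placebo patients who completed | Not addressed |
| 4.7 | Not addressed | Optional, after the 28-day visit |
| 7.5 | Invitation at the end of the 6-month phase | Mentions unblinding at discontinuation, without timing |
| 7.21 | Nobody failing a phase's entry criteria | Not addressed |
| 4.4 and Table 13B | Baseline is the blinded final or Month 6 visit; entry within 2 weeks of Month 6, with an eligibility check | Not addressed |

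On entry, 4.3 and 7.6 stand against the rest. On timing, 4.3 and 7.6 stand against 4.7. Section 7.6.1 expressly bars open-label entry after emergency unblinding; 7.6 has no matching sentence for ordinary early termination.

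**2. Inputs** (Sections 7.5, 17 and 17.1): 1:1 allocation, 20 per arm; one-sided α = 0.05; chi-square or Fisher's exact test; power illustration 1/20 on placebo against 8/20 on everolimus with stated power 0.81; overall drop-out about 10%; reporting threshold 10 points.

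**3. The plan's own power figure.** Exact power of the one-sided Fisher test is the sum, over placebo counts a and everolimus counts b from 0 to 20, of Bin(a; 20, 0.05) × Bin(b; 20, 0.40), counting only pairs with p ≤ 0.05. This gives 0.808, which reproduces 0.81. (The uncorrected chi-square gives 0.897 and a pooled normal approximation 0.866.)

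**4. Shift per exit.** 1/20 = 5 points. Take 3/20 on everolimus against 1/20 on placebo: 15% − 5% = 10 points, reportable.
- One added placebo exit: 15% − 10% = 5 points, below the threshold.
- Two added: 15% − 15% = 0.

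For scale, 10% drop-out is 0.10 × 20 = 2 patients per arm if equal between arms.

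**5. Effect at the plan's power scenario.** The documents give no rate of such exits, so k is an assumption, shown as a range. The everolimus rate stays at 40%, the placebo rate becomes (1 + k)/20, and every added exit is taken to count in the comparison being tested.

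| Added placebo exits k | Placebo rate | Fisher power | One-sided p if 8/20 against (1 + k)/20 is observed |
|---|---|---|---|
| 0 | 5% | 0.81 | 0.010 |
| 1 | 10% | 0.62 | 0.032 |
| 2 | 15% | 0.44 | 0.078 |
| 3 | 20% | 0.29 | 0.150 |
| 4 | 25% | 0.18 | 0.250 |

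If completers only are admitted everywhere, this mechanism supplies no added exits and the first row stands.

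**6. Which comparison is touched.** Section 7.7.6 requires the reason for discontinuation to be recorded and lists adverse events separately from withdrawal of consent and other reasons. An exit made only to reach active drug therefore enters drop-out for any reason and its Kaplan-Meier analysis. It enters the primary endpoint only if a side effect is recorded as the reason.

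**The case against.** The strongest reply is that the protocol, read as a whole, already closes the route. An eligibility criterion governs an invitation sentence; 7.21 says so in effect; and Table 13B schedules an eligibility check at an open-label baseline tied to Month 6, which a Month 2 leaver would not have. The unblinding procedure is in the Manual of Procedures, which is not available here and may be clear. This largely stands: a reader might infer that the protocol gives early leavers open-label drug, and the documents taken together do not support that. It does not remove the conflict within 4.3 and 7.6, or the separate conflict with 4.7 over when early terminators learn their arm.

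Three further points stand:
- A reader might infer direct bias in the primary endpoint. The family described above leaves for want of side effects or benefit, which is not a side-effect drop-out.
- A reader might infer that the incentive acts only on placebo. The choice is made blind, and a family on everolimus may guess wrongly, stop and get nothing further. A placebo excess needs better-than-chance guessing.
- Section 5.1 is a retention measure. Awareness of the open-label phase is meant to keep families in, and under a completers-only rule it would.

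Finally, the 5-point step is simple arithmetic for any exit at this sample size; it is not evidence that such exits will occur.

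**Conclusion.** The contradiction is real and is in the current text. Its statistical effect is conditional. It arises only if a site acts on 4.3 or 7.6, families guess placebo better than chance, and some leave for that reason. It then falls on drop-out for any reason, and on drop-out due to side effects only where a side effect is recorded.

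The size cannot be estimated from the documents. With 20 per arm each added placebo exit costs 5 points, and two cancel a 10-point difference. In the plan's own 5% against 40% scenario, one or two exits counted in the comparison lower power from 0.81 to 0.62 or 0.44. The direction is towards similar drop-out, so an excess on everolimus could be masked. The stronger statement, that placebo drop-out is inflated by design, is not supported. Section 17 calls the analyses predominantly descriptive, which limits the inferential stakes, but observed drop-out differences are what a descriptive safety report will show.

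**What to change.** 1. Reconcile 4.3, 7.6, 4.6.3 and 4.7 so that they state one rule on who is invited to the open-label phase, and align the synopsis, 4.4, 7.5, 7.21 and Table 13B with it. Which rule applies is for the sponsor to decide.
2. State one rule, in the same sections, on when early terminators are unblinded.
3. Require the drop-out reason, including whether it is a side effect, to be recorded and dated before the code is broken. The instruction in 7.6 to obtain the assignment before early termination must be reordered to match.

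A rule that stopping drug while still attending visits counts as completing the blinded phase should not be added as part of this repair. No passage supports it, and it sits badly with 6.3.12 and 7.7.3, which discontinue from the study patients with a dose delay, or recovery from toxicity, of 6 weeks or more.

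The cost is a few sentences, a matching check of the Manual of Procedures, a dated field on the discontinuation form, and the amendment review required by Section 18. No sample-size change or added assessment is needed.

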4.4 Open Label Phase

Individuals in the placebo group will be invited to enter the 6-month open-label extension trial that will follow the same schedule as the blinded treatment phase. The final visit, or the Month 6 visit, in the blinded treatment phase will serve as the baseline visit of the open label phase if the participant chooses to enter the open label phase. Safety labs obtained at the end of the blinded phase will be used as baseline safety labs for the open-label phase. Similarly, the scores from the patient's developmental assessments will be used as both the 6-month blinded treatment phase data, and the baseline open-label phase data. Study staff should be prepared to dispense open label medication at this visit. If the patient is unable to enter the open-label phase at the final visit of the blinded treatment phase, the patient can come back within 2 weeks (+/- 2 weeks) of this visit date. Treatment, assessments, and outcomes of the open-label phase will also be identical to the double-blind phase.

The next visit will be the Month 1 visit. A PK sample, as well as specified safety labs, will be drawn on site and sent to LabConnect LLC. If the participant receives a dose adjustment at the time of this visit, study staff will work with the participant/family to get another sample taken at the study site or locally by a trained phlebotomist. The Month 3 visit and the Month 6 visit will include safety labs, developmental testing, optional EEG/AEP and eye tracking procedures, physical and neurological exams, vital signs, and other study questionnaires. A PK sample may also be collected from a patient experiencing an adverse event or side effect. The decision to obtain this sample will be made by the site physician.

The Month 2, Month 4, and Month 5 visits can be in person or by-phone if that is preferred by the family. If performed by phone, a phone interview will be performed to collect safety and other data, review AEs, and assess changes in mood or behavior. All applicable CRFs will be completed.

If unforeseen circumstances (i.e., unexpected personal reasons) prevent the patient from complying with the established visit schedule, the site can re-schedule the visit (within ± 14 days of the expected visit date). The reason(s) for any visit or treatment delays will be documented in the CRF for the appropriate visit. All on-site visits (month 1, month 3, and month 6) must be completed by the participant, and any missed visits would warrant termination from the study. Under extenuating unforeseen circumstances, visits 3, 5, 8 (months 1, 3, and 6) can be conducted by phone/video conference as a modified visit as to still capture obtainable data and maintain patient safety. A summary of the neuropsychological results may be made available at study completion.

At the final visit of the open label phase, or the 6 month visit, participants will exit the trial. As done in the blinded treatment phase, they will receive a letter

4.5 Follow-Up Phase

All patients will have a follow-up phone call scheduled 28 days (± 14 days) after the last dose of the study treatment to follow for AEs and SAEs that may have occurred after discontinuation from the study treatment. See section 6.3.15 for additional details.

4.6 Patient Selection and Inclusion/ Exclusion Criteria

Patients must have screening evaluations performed within the 6 weeks of the baseline visit and must still meet all inclusion and exclusion criteria at the time of the baseline visit. Results of all screening evaluations, which ensure that all inclusion and exclusion criteria have been satisfied, must be reviewed by the site's Principal Investigator or his/her designee prior to enrollment of that patient. In addition, the patient must be thoroughly informed about all aspects of the study, including the study visit schedule and required evaluations and all regulatory requirements for informed consent. The written informed consent must be obtained from the patient prior to any screening activities. The following criteria apply to all patients enrolled onto the study, unless otherwise specified.

4.6.1 Double-Blind Inclusion Criteria

- 1. Male and female outpatients between 5 and 45 years of age (inclusive);
- 2. Pathogenic PTEN mutation confirmed by clinical genetic testing;
- Participant must be able to complete one of the following three standardized assessments: Conners'
 Continuous Performance Tasks (CPT-3), Stanford Binet (SB-5; working memory), or the Purdue Pegboard
 Test:
- 4. Performance below the age-adjusted population mean on at least one of the above standardized measures: attention (CPT-3, mean reaction time), working memory (SB5, working memory subscale), or fine motor skills (Purdue Pegboard Test; either dominant, non-dominant, or both hands);
- 5. Adequate bone marrow function as shown by:
 - a. Platelets \geq 80,000/mm³
 - b. Absolute neutrophil count ≥ 1,000/mm³
 - c. Hemoglobin ≥ 9 g/dL;
- 6. Adequate liver function as shown by:
 - a. Total serum bilirubin <1.5 x ULN
 - b. AST and ALT levels < 2.5 x ULN
 - c. INR ≤2;
- 7. Adequate renal function: serum creatinine < 1.5 x ULN;
- 8. Signed informed consent obtained prior to any screening procedures;
- 9. Individuals on psychotropic and anti-epileptic medications should maintain a stable dose for at least 2 months prior to the screening visit;
- 10. Negative serum pregnancy test for females at screening and no plans to become pregnant or conceive a child while participating in the study. The effects of mTOR inhibitors on the developing fetus at the doses used in this study are unknown. For this reason, women of child-bearing potential and men must agree to use adequate contraception prior to study entry and for the duration of the study. Estrogen-containing oral contraceptives are not recommended in women enrolled in this study. Abstinence or two effective non-estrogen or barrier methods of contraception (such as condom + spermicidal foam) must be used:
- 11. Medically stable with no active medical problem such as unstable seizure or cardiovascular disease as evidenced by a history:
- 12. No anticipated changes in the frequency and intensity of existing interventions such as behavioral and developmental treatments, in home services, and speech therapy;
- 13. No planned changes in school placement;
- 14. For individuals under 18 or who are otherwise incapable, there must be an available caregiver who can reliably bring subject to clinic visits and provide trustworthy data;
- 15. Able to communication fluently in English.

